11.1. Adverse Event Definitions

11.1.1. Adverse Event

Any untoward medical occurrence, unintended disease or injury, or untoward clinical signs (including abnormal laboratory findings) in subjects, users or other persons, whether or not related to the investigational medical device. (ISO 14155:2011 3.2)

Note 1: This definition includes events related to the investigational medical device or the comparator.

Note 2: This definition includes events related to the procedures involved.

PR-NV16099	Version C	Page 98 of 144	Medtronic
------------	-----------	----------------	-----------

Note 3: For users or other persons, this definition is restricted to events related to investigational medical devices.

11.1.2. Serious Adverse Event

Adverse Event that

- a) Led to death, injury or permanent impairment to a body structure or a body function
- b) Led to a serious deterioration in the health of the subject, that either resulted in:
 - a. A life-threatening illness or injury, or
 - b. A permanent impairment of a body structure or a body function, or
 - c. In-patient hospitalization or prolongation of existing hospitalization, or
 - d. Medical or surgical intervention to prevent life-threatening illness or injury or permanent impairment to a body structure or a body function,
- Led to fetal distress, fetal death or a congenital abnormality or birth defect (ISO 14155:2011 3.37)

Note: Planned hospitalization for a pre-existing condition, or a procedure required by the Clinical Investigation Plan, without serious deterioration in health, is not considered a SAE.

11.1.3. Adverse Device Event

Adverse event related to the use of an investigational medical device. (ISO 14155:2011 3.1) The investigational medical device for this study is the Pipeline[™] Vantage Device used during the study procedure (Day 0).

Note 1: This definition includes any adverse events resulting from insufficiencies or inadequacies in the IFU, the deployment, implantation, installation, operation, or any malfunction of the investigational medical device.

Note 2: This definition includes any event resulting from use error or intentional abnormal use of the investigational medical device.

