9.5.6. No Treatment of an Eligible Subject with the Pipeline[™] Vantage Device

In the event that the subject was confirmed to be eligible for the study at baseline, signed informed consent, but the target intracranial aneurysm is not treated with the Pipeline[™] Vantage Device at the initially scheduled procedure, the subject may be brought in later to undergo the Pipeline[™] Vantage Device. In this case:

- In the event the subject does not meet protocol specified PRU value range (≥60 and ≤200) or TEG value range (>30% to <90%) on the day of the procedure, the procedure should be delayed (and no puncture at the arterial access site performed) until a protocol specified therapeutic range for PRU/TEG is achieved. The day of the puncture at the arterial access site is considered day 0.
- 2) In cases where PRU/TEG criteria is met and puncture at the arterial access site is performed, and the aneurysm is not able to be accessed or a study device unable to be deployed, the reasons of the inaccessibility of the aneurysm or study device failing to deploy (incomplete treatment) will be captured. Any alternate treatments if received will be captured. Such subjects will not be included in the per-protocol analysis. In cases where the subject is brought back at a later time and undergoes a second procedure with the study device, the date of the first intervention will be considered Day 0. The second intervention (if successful) will not be considered a retreatment. The subject must be brought back for the second intervention within 6 weeks of the initial attempted treatment.

PR-NV16099

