9.8. Retreatment

At the Investigator's discretion, the target aneurysm may be retreated at any time during the study. The retreatment procedure can include any endovascular or surgical intervention including the implant of the Pipeline[™] Vantage Device. In such situations, the date that the subject receives the initial Pipeline[™] Vantage Device implant (and not the date of the retreatment) will be considered Day 0.

Reason(s) for retreatment of aneurysm shall be documented:

- Device Movement
 - Foreshortening (Peri-procedural or Delayed)
 - Migration
- Aneurysm Growth
- Aneurysm Rupture
- Aneurysm Non-Occlusion
- Insufficient Neck Coverage

Type of Retreatment will be documented:

- Planned
- Unplanned

A retreatment will be considered an "Unscheduled Visit" and subjects will be required to undergo the following study assessments:

- Full neurological exam and assessment of aneurysm symptoms (new, worsened, improved, stable)
- Record concomitant and protocol-specified medications
- Imaging (per standard of care)
- NIHSS
- mRS assessment to be carried out by a certified independent assessor at site
- Assessment of Adverse events

		· · · · · · · · · · · · · · · · · · ·	and the second sec
PR-NV16099	Version C	Page 83 of 144	Medtronic

Data will be collected for all retreatment procedures in the Retreatment eCRFs. Retreatments should be reported as an SAE.

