11.1.8. Causality Assessment of Events

The relationship between the occurrence of each adverse event to the following will be assessed:

- Use of the medical device for this study, Pipeline[™] Vantage Device
- Index study procedure (on Day 0) involving initial application of the investigational medical device, and therefore not to any other procedures or treatments applied later during the clinical investigation (e.g., surgical procedures to treat SAEs).
- Use of antiplatelet therapy.

PR-NV16099	Version C	Page 100 of 144		Medtronic
------------	-----------	-----------------	--	-----------

The occurrence of each adverse event shall be assessed and categorized according to five different levels of causality for which the following definitions shall be used to assess the relationship of the adverse event to the investigational medical device, or index procedure, or use of DAPT:

1. Not Related:

Relationship to the device or procedures can be excluded when:

- the event is not a known side effect of the product category the device belongs to or of similar devices and procedures;
- the event has no temporal relationship with the use of the investigational device or the procedures;
- the serious event does not follow a known response pattern to the medical device (if the response pattern is previously known) and is biologically implausible;
- the discontinuation of medical device application or the reduction of the level of activation/exposure when clinically feasible and reintroduction of its use (or increase of the level of activation/exposure), do not impact on the serious event;
- the event involves a body-site or an organ not expected to be affected by the device or procedure;
- the event can be attributed to another cause (e.g. an underlying or concurrent illness/clinical condition, an effect of another device, drug, treatment or other risk factors);
- the event does not depend on a false result given by the investigational device used for diagnosis*, when applicable [*If an investigational device gives an incorrect diagnosis, the subject might, for example, receive an unnecessary treatment and incur all the risks that accompany that treatment, or might be incorrectly diagnosed with a serious disease. In other cases, the subject might not receive an effective treatment (thereby missing out on the benefits that treatment would confer), or might not be diagnosed with the correct disease or condition];

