- In order to establish the relatedness, not all the criteria listed above might be met at the same time, depending on the type of device/procedures and the serious event.

The Investigators shall distinguish between the adverse events related to the investigational device and those related to the procedures (any procedure specific to the clinical investigation).

An adverse event can be related both to procedures and the investigational device.

Complications of procedures are considered not related if the said procedures would have been applied to the subjects in the absence of investigational device use/application.

In some particular cases the event may be not adequately assessed because information is insufficient or contradictory and/or the data cannot be verified or supplemented. The Investigators will make the maximum effort to define and categorize the event and avoid these situations. Where the Sponsor remains uncertain about classifying the adverse event, it should not exclude the relatedness and classification of the event should be noted as "possible".

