13.8.4. Adverse Events

Adverse events will be coded according to the Medical Dictionary for Regulatory Activity (MedDRA) system dictionary.

CEC adjudicated data Tables to summarize the incidence rates will be created for each of the following groups: (At 1 year, 1- 2 years, and 2- 3 years)

- Adverse events (non-Serious) related to intervention (Procedure, anti-platelet therapy (APT)), Causal, Probable
- Serious adverse events related to Intervention (Procedure, APT)- Causal, Probable
- Adverse device effects (Non-SAE Related to Study Device- causal, probable)
- Serious adverse device effects (SAE Related to Study Device-causal, probable)
- Unanticipated serious adverse device effects (USADE)/UADE
- Adverse events by severity (Mild, Moderate and Severe) related to Device, Procedure or APT (causal, probable)

PR-NV16099

Version C

14. Ethics

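### Tying the definitions to Day 0 leaves a Pipeline Vantage placed at a second attempt outside both the device-effect and procedure-related classes, and one placed at retreatment outside the device-effect class

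*Combined protocol and SAP*

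**What the plan says.** Section 11.1.3 defines an adverse device effect (ADE) by reference to the investigational device, which it then identifies as the Pipeline "Vantage Device used during the study procedure (Day 0". The serious and unanticipated serious categories (SADE, USADE) in 11.1.4 and 11.1.5 build on that definition. Section 11.1.8 lists what each event's causality is assessed against. The procedure item names the index procedure on Day 0, "and therefore not to any other procedures or treatments applied later during the clinical investigation".

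The study device can be placed after Day 0 in two ways. Under 9.5.6, if the first attempt fails after arterial puncture, the subject may return: "The subject must be brought back for the second intervention within 6 weeks of the initial attempted treatment". When the subject "undergoes a second procedure with the study device, the date of the first intervention will be considered Day 0", and a successful second intervention is not counted as a retreatment. Under 9.8, "The retreatment procedure can include any endovascular or surgical intervention including the implant of the" Pipeline Vantage device, and Day 0 stays at the initial implant.

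The opening of Section 11 tells site investigators to categorise events with the definitions in 11.1 and 11.3. Section 13.8.4 then tabulates CEC-adjudicated events by relatedness, including "Serious adverse device effects (SAE Related to Study Device-causal, probable)".

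**The concern.** The labels that attribute harm to the device or its placement are tied to a date, while the protocol allows the device to be placed on other dates. The second attempt is the clearest case. The only implant such a subject carries was not used on Day 0, and the procedure that placed it is neither the index procedure nor a retreatment. A site that follows 11.1.3 and the Day 0 item literally would not class thrombosis of that implant as an ADE, nor a dissection during its placement as procedure-related. A reader who follows the glossary would do the opposite. In a single-arm study of a permanent implant, the rates of device- and procedure-related events should not depend on which section the assessor had open.

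**Working it through.** No stated figure needs reproducing. The check sets the passages side by side and then gauges the scale.

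**Literal application of 11.1.3 and the Day 0 item of 11.1.8**

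| Vantage placed at | Day 0 is | Device used on Day 0 (11.1.3)? | Day 0 index procedure (11.1.8)? |
|---|---|---|---|
| Index procedure | the same day | yes | yes |
| Second attempt (9.5.6) | the failed first attempt | no | no |
| Retreatment (9.8) | the initial implant | no | no, by the stated exclusion of later procedures |

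The glossary offers no way round this. It defines the index procedure as the first intended procedure with a successful arterial puncture, which is the failed attempt. Section 9.9 refers to subsequent attempts after the index procedure, so they are expected. The Day 0 item is also unclear within itself. It describes the index procedure as the initial application of the device, but if the aneurysm could not be reached on Day 0, the device may first have been applied at the second attempt.

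**Text that points the other way**

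- The glossary definition of an ADE refers to use of an investigational device, with no date.
- The device item in 11.1.8 carries no date.
- The closing text of 11.1.8 asks investigators to separate device-related events from "those related to the procedures (any procedure specific to the clinical investigation)". A second attempt under 9.5.6 fits that description.

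The protocol therefore has two incompatible scopes for the same classification.

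**What does not depend on the Day 0 wording**

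- All adverse events are collected through study exit (Section 11), and retreatments are reported as serious adverse events (9.8).
- All serious adverse events reach the sponsor within 24 hours, whatever their relatedness (11.2, Table 11-1).
- The UADE definition (11.1.6) and device deficiency (11.3) have no Day 0 limit.
- Device thrombosis, parent artery stenosis, device movement, dissection and thromboembolic complications are events of interest (10.1), which the CEC adjudicates for each subject (12.1).
- The primary safety endpoint (5.1.1.1.2) does not use relatedness.

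**Scale, per 100 treated subjects**

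- Failed deployment in SHIELD (4.2.7): 204 − 200 = 4, and 4/204 = 1.96%, or about 2 subjects.
- Retreatment in PREMIER (4.2.5): 4/139 = 2.88%, or about 3 subjects.
- If a share *f* of both groups receives a further Pipeline Vantage, the exposed number is *f* × (1.96 + 2.88) = *f* × 4.84. With *f* = 0 this is 0. With *f* = 1 it is 4.84, about 5.
- PFLEX (4.2.8) had 50 of 50 deployments succeed and no retreatments, which gives 0.

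These are subjects exposed to the ambiguity, not subjects with an affected event.

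**The case against.** The strongest reply has four parts.

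1. The sentence in 11.1.3 may be meant only to name the product, and the glossary definition is undated. That reading is possible. But Section 11 sends sites to the 11.1 definitions, and the sentence does carry the date.
2. The exclusion of later procedures in 11.1.8 is deliberate; its example is surgery to treat a serious adverse event. This stands for retreatment, which may be any endovascular or surgical intervention. Extending procedure causality to retreatments that do not use the study device would be a preference, not a correction. It does not stand for the second attempt, which is the delayed placement of the study device and which 9.5.6 says is not a retreatment.
3. The 13.8.4 tables use CEC-adjudicated data. The CEC works to a charter that is not among the documents, so it is not shown that the tables inherit the Day 0 limit. This stands, and the effect on the tables is conditional.
4. Nothing is lost from the database. This also stands.

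A reader might go further and infer that expedited reporting or the primary safety result is compromised. The documents do not support that: serious events are notified regardless of relatedness, UADE reporting is not tied to Day 0, and the primary endpoint ignores relatedness. Only the USADE label is touched.

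**Conclusion.** The concern holds as a contradiction in the classification rules. Followed literally, 11.1.3 and the Day 0 item of 11.1.8 exclude an event caused by a second-attempt device from both the ADE and the procedure-related classes, and exclude an event caused by a Vantage placed at retreatment from the ADE class. The exposure is confined to relatedness labels (ADE, SADE, USADE, procedure-related) and to 13.8.4 so far as those tables follow them.

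The size is small: roughly 0 to 5 exposed subjects per 100. This assumes that SHIELD's deployment failures stand in for failed first attempts here, that PREMIER's one-year retreatment rate carries over, that the two groups do not overlap, and that between 0 and 100% of them receive a further Vantage. Follow-up here runs to three years, so a one-year retreatment rate may be low.

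A reader might infer that at least one affected subject is nearly certain in 100. Such a calculation would count every failed attempt and every retreatment, whether or not another Vantage followed. The documents give no rate for that step. Nor do they establish that these subjects carry a higher risk. Section 10.2 cites a technically difficult procedure as a predictor of perioperative complications, but says nothing of later attempts or retreatment.

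**What to change.** - In 11.1.3, define the investigational device as any Pipeline Vantage attempted or implanted in the study, whether at the index procedure, a second attempt under 9.5.6 or a retreatment under 9.8.
- In 11.1.8, assess procedure causality against the index procedure and any second attempt under 9.5.6. Align the Day 0 item with the closing text of that section and with the glossary.
- Add one field to the eCRF and CEC form that records, for each related event, the procedure to which it is attributed.
- In 13.8.4, include all such events and show index-only rates as a sub-row. Confirm that the CEC charter uses the same scope.

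The cost is wording in two sections, one data field and a sub-row in the tables. No treatment rule changes. The downside is that related-event rates may look slightly less favourable; the index-only sub-row keeps the narrower figure visible.

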11.1.4. Serious Adverse Device Event

Adverse device effect that has resulted in any of the consequences characteristic of a SAE. (ISO 14155:2011 3.36)

PR-NV16099

11.1.5. Unanticipated Serious Adverse Device Event (USADE)

Serious adverse device effect which by its nature, incidence, severity or outcome has not been identified in the current version of the risk analysis report. (ISO 14155:2011 3.42)

Note: Anticipated serious adverse device effect (ASADE) is an effect which by its nature, incidence, severity or outcome has been identified in the risk analysis report.

11.1.6. Unanticipated Adverse Device Event

Serious adverse effect on health or safety or any life-threatening problem or death caused by, or associated with, a device, if that effect, problem, or death was not previously identified in nature, severity, or degree of incidence in the investigational plan or application (including a supplementary plan or application), or any other unanticipated serious problem associated with a device that relates to the rights, safety, or welfare of subjects. (21 CFR 812.3 (s))

11.1.7. Event Severity

The severity of an adverse event is a qualitative judgment of the degree of intensity, as determined by the Principal Investigator or as reported by the subject. The severity of the AE should be evaluated according to the following scale:

- Mild: No limitation of usual activities, no therapy or only symptomatic therapy required to treat the injury or illness.
- Moderate: Some limitation of usual activities or specific therapy is required.
- Severe: Inability to carry out usual activities, hospitalization, emergency treatment, life-threatening events, or death.

11.1.8. Causality Assessment of Events

The relationship between the occurrence of each adverse event to the following will be assessed:

- Use of the medical device for this study, Pipeline[™] Vantage Device
- Index study procedure (on Day 0) involving initial application of the investigational medical device, and therefore not to any other procedures or treatments applied later during the clinical investigation (e.g., surgical procedures to treat SAEs).
- Use of antiplatelet therapy.

PR-NV16099	Version C	Page 100 of 144		Medtronic
------------	-----------	-----------------	--	-----------

The occurrence of each adverse event shall be assessed and categorized according to five different levels of causality for which the following definitions shall be used to assess the relationship of the adverse event to the investigational medical device, or index procedure, or use of DAPT:

1. Not Related:

Relationship to the device or procedures can be excluded when:

- the event is not a known side effect of the product category the device belongs to or of similar devices and procedures;
- the event has no temporal relationship with the use of the investigational device or the procedures;
- the serious event does not follow a known response pattern to the medical device (if the response pattern is previously known) and is biologically implausible;
- the discontinuation of medical device application or the reduction of the level of activation/exposure when clinically feasible and reintroduction of its use (or increase of the level of activation/exposure), do not impact on the serious event;
- the event involves a body-site or an organ not expected to be affected by the device or procedure;
- the event can be attributed to another cause (e.g. an underlying or concurrent illness/clinical condition, an effect of another device, drug, treatment or other risk factors);
- the event does not depend on a false result given by the investigational device used for diagnosis*, when applicable [*If an investigational device gives an incorrect diagnosis, the subject might, for example, receive an unnecessary treatment and incur all the risks that accompany that treatment, or might be incorrectly diagnosed with a serious disease. In other cases, the subject might not receive an effective treatment (thereby missing out on the benefits that treatment would confer), or might not be diagnosed with the correct disease or condition];
- harms to the subject are not clearly due to use error;
- In order to establish the non-relatedness, not all the criteria listed above might be met at the same time, depending on the type of device/procedures and the serious event.

PR-NV16099	
------------	--

2. Unlikely:

The relationship with the use of the device seems not relevant and/or the event can be reasonably explained by another cause, but additional information may be obtained.

3. Possible:

The relationship with the use of the investigational device is weak but cannot be ruled out completely. Alternative causes are also possible (e.g., an underlying or concurrent illness/clinical condition or/and an effect of another device, drug or treatment). Cases were relatedness cannot be assessed or no information has been obtained should also be classified as possible.

4. Probable:

The relationship with the use of the investigational device seems relevant and/or the event cannot reasonably explain by another cause, but additional information may be obtained.

5. Causal relationship:

The adverse event is associated with the investigational device or with procedures beyond reasonable doubt when:

- the event is a known side effect of the product category the device belongs to or of similar devices and procedures;
- the event has a temporal relationship with investigational device use/application or procedures;
- the event involves a body-site or organ that:
 - the investigational device or procedures are applied to;
 - the investigational device or procedures have an effect on:
- the adverse event follows a known response pattern to the medical device (if the response pattern is previously known);
- the discontinuation of medical device application (or reduction of the level of activation/exposure) and reintroduction of its use (or increase of the level of activation/exposure), impact on the serious event (when clinically feasible);

ADVANCE Clinica	al Investigation Plan		
PR-NV16099	Version C	Page 102 of 144	Medtronic

- other possible causes (e.g. an underlying or concurrent illness/clinical condition or/and an effect of another device, drug or treatment) have been adequately ruled out;
- harm to the subject is due to error in use;
- the event depends on a false result given by the investigational device used for diagnosis*, when applicable;
- In order to establish the relatedness, not all the criteria listed above might be met at the same time, depending on the type of device/procedures and the serious event.

The Investigators shall distinguish between the adverse events related to the investigational device and those related to the procedures (any procedure specific to the clinical investigation).

An adverse event can be related both to procedures and the investigational device.

Complications of procedures are considered not related if the said procedures would have been applied to the subjects in the absence of investigational device use/application.

In some particular cases the event may be not adequately assessed because information is insufficient or contradictory and/or the data cannot be verified or supplemented. The Investigators will make the maximum effort to define and categorize the event and avoid these situations. Where the Sponsor remains uncertain about classifying the adverse event, it should not exclude the relatedness and classification of the event should be noted as "possible".

